6.5 SAFETY ANALYSES

The safety analyses population will be based on all enrolled patients grouped according to the actual treatment received. For Arm C patients, all safety data reported up to the day prior to switching will be included in the "control arm" safety summaries, and all safety data reported on or after the date of switching to active treatment will be reported separately.

Safety will be assessed for Arms A, B, and C and separately for Arm D through descriptive summaries of adverse events, laboratory test results (serum chemistry and hematology, including complete blood count with differential), ECGs, vital signs, and antibodies to emicizumab and FVIII.

To evaluate the overall safety of prophylactic emicizumab compared with no prophylaxis, the incidence of adverse events will be summarized and presented by System Organ Class mapped term, appropriate thesaurus level, and toxicity grade for each treatment arm.

For clinical laboratory data, summary statistics will be presented by treatment arm. In addition, shift tables describing changes from baseline will be presented using the WHO toxicity grading scale.

Data on the effect of immunogenicity (anti-emicizumab antibodies) on safety, efficacy, and/or clinical pharmacology and pharmacokinetics will be summarized adopting standard language/terminology (Shankar et al. 2014).

Although this is an open-label study, Sponsor personnel will not have access to safety summaries by treatment arm prior to the formal reporting of the study results. HCPs at participating study sites, as well as the Sponsor's drug safety and medical monitoring staff, will have access to the treatment assignments of patients for safety monitoring purposes only.

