Safety Objectives: For Arms A, B, and C: 
• To evaluate the overall safety of prophylactic emicizumab compared with no prophylaxis in patients with hemophilia A For Arm D: 
• To evaluate the overall safety of prophylactic emicizumab treatment in pediatric patients with hemophilia A and inhibitors	Safety Endpoints For Arms A, B, C, and D: 
• The incidence and severity of adverse events• The incidence and severity of thromboembolic events• Incidence and severity of thrombotic microangiopathy• Changes in physical examination findings and vital signs• Incidence of laboratory abnormalities• Incidence and severity of injection-site reactions• Incidence of adverse events leading to drug discontinuation• The incidence of severe hypersensitivity, anaphylaxis, or anaphylactoid reactions• The incidence and clinical significance of anti-emicizumab antibodies

Table 2 Objectives and Corresponding Endpoints (cont.)

Objectives	Corresponding Endpoints
Pharmacokinetic Objective:	Pharmacokinetic Endpoints
For Arms A, B, C, and D: 
To characterize the exposure (trough plasma concentration) of emicizumab in patients treated on QW or Q4W dosing	For Arms A and D: 
Trough plasma concentrationThe plasma samples will be collected at the scheduled timepoints below: For patients treated on weekly dosing schedule:
Every week during Weeks 1–4 on emicizumabEvery 2 weeks during Weeks 5–8 on emicizumabEvery 4 weeks during Weeks 9–24 on emicizumabEvery 8 weeks during Weeks 25–48 on emicizumabEvery 12 weeks thereafter while on emicizumab, until the end of the study or after the last patient completes 24 weeks treatment of emicizumab, whichever occurs first For Arms B and C: For patients treated on every 4 weeks dosing schedule: 
Every week during Weeks 1–4 on emicizumabEvery 4 weeks during Weeks 5–24 on emicizumabEvery 12 weeks thereafter while on emicizumab, until the end of the study or after the last patient completes 24 weeks treatment of emicizumab, whichever occurs first

Adapted Inhib-QoL =Inhibitor-Specific Quality of Life (with Aspects of Caregiver Burden); FVIII =factor VIII; HRQoL =health-related quality of life; PD =pharmacodynamic; Q4W =every 4 weeks; QW =every week.

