Throughout the study, biomarkers related to thromboembolism (e.g., D-dimer, prothrombin 1 + 2 fragment) and emicizumab trough concentrations will be collected as per the schedule of assessments. Immunologic biomarkers (i.e., anti-emicizumab antibodies and anti-FVIII antibodies) will also be measured (see [Appendix 2](#)).

Exploratory PD biomarkers (e.g., aPTT, FVIII activity, thrombin generation assay) will be collected as per the schedule of assessments. As values for some of these tests are normalized by low plasma concentrations of emicizumab, a variety of assay formats (one stage, chromogenic) and modifications (pre-dilution of patient plasma) will be investigated for assessment of PD response at higher emicizumab plasma concentrations. However, it is not expected that these biomarkers will be used to guide dosing or the selection of patients to be treated with emicizumab. Rather, these biomarkers may be used to identify a future assay for the monitoring of emicizumab activity. In addition, factor IX (FIX) and FX antigen levels will be measured.

Physical examinations, vital signs assessments, ECGs, and laboratory assessments will be collected as per the schedule of assessments and will be the same for all patients, with the exception that emicizumab PK and ADAs will not be measured in patients in Arm C prior to switch to emicizumab treatment. Adverse events will be captured as they occur for the duration of the study.

All patients who receive emicizumab in the study will undergo PK assessments. Based on clinical experience in the ongoing Phase I/II clinical studies with the treatment of over 80 breakthrough bleeds in patients receiving emicizumab with either FVIII or bypassing agents, FVIII, aPCC, or rFVIIa do not interfere with emicizumab PK assessments and no safety signals have been observed when breakthrough bleeds were treated with standard-of-care regimens during Phase I and Phase I/II studies. Therefore, no washout period is required prior to first emicizumab dose in this study, with the exception of patients who were previously receiving ITI in whom a 72-hour washout period is required prior to the first emicizumab administration.

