Appendix 1-A (cont.) Schedule of Assessments

Schedule of Assessments—Arm C (Screening to Switch to Emicizumab)								
	Screening ^a	Wk 1	Wk 5	Wk 9	Wk 13	Wk 17	Wk 21	Daily/weekly ^b
Informed consent ^e	x							
Inclusion/exclusion criteria	x							
Medical history and demographics ^f	x							
Physical examination (including weight) ^g	x	x						
Vital signs ^h	x	x ^h	x	x	x	x	x	
Height	x							
Serum pregnancy test ⁱ	x	x						
Urine pregnancy test ⁱ		x						
Concomitant medications ^j	x	x	x	x	x	x	x	
ECG ^k	x	x ^k						
Safety laboratory assessments ⁱ	x ⁱ	x						
Anti-FVIII antibodies	x							
Bleed medication questionnaire ^l								x
Bleed/injection data review ^s		x	x	x	x	x	x	
Adverse events ^m		x	x	x	x	x	x	
HRQoL and health status ^o		x			x			
PD biomarkers assessment ^q		x						

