Appendix 1-A (cont.) Schedule of Assessments

Disc =discontinuation; eCRF=electronic Case Report Form; ET=early termination; F/U=follow-up; FVIII=factor VIII; HRQoL=health-related Quality of Life; IMP=investigational medicinal product; Adapted Inhib-QoL =Inhibitor-Specific Quality of Life (with Aspects of Caregiver Burden); PD=pharmacodynamic; PK=pharmacokinetic; Q8W=every 8 weeks; Q12W=every 12 weeks; study comp.=study completion; Wk=week.

Notes: All assessments should be performed within \pm 2 days of the scheduled visit for the first 3 months, then \pm 7 days thereafter. PD and PK (trough) samples will be collected within \pm 2 days of the scheduled visit and linked to the timing from the dose. Clinic visits should coincide with the day of emicizumab dosing, and on those days the dose should be administered after blood draws and other assessments are conducted.

Unscheduled assessments may be performed at the discretion of the investigator and as clinically indicated. Except for the bleed/injection questionnaire, HRQoL, and health status, all other patient data will be collected during office or nurse visits. Evaluation at Week 25 or 49 will occur after a full 24 or 48 weeks in the study, respectively. Study completion evaluation occurs when a patient discontinues emicizumab or transitions into another study.

- ^a Screening may occur up to 4 weeks before Week 1 dosing.
- ^b Patients will complete the bleed/medication questionnaire at least weekly and at the time of a bleed, or when they take a hemophilia-related medication (including emicizumab). Arm B patients should indicate at least weekly whether or not they had a bleed.
- ^c There will be an Extension Phase in this study for all patients who have completed at least 52 weeks of treatment with prophylactic emicizumab and are still deriving clinical benefit. The study will be extending for 3 years after the last Arm D patient completes 1 year of treatment *and patients still having clinical benefit are transferred to a post-trial continued access solution per Roche Global Policy on Continued Access to Investigational Medicinal Products (Section 4.3.4). The study will end earlier, before 3 years after the last Arm D patient completes 1 year treatment, should the post-trial continued access solution be available earlier.*

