- ^d In the event a patient discontinues emicizumab early before the study completion, an early discontinuation safety follow-up visit should be performed 24 weeks after discontinuation of emicizumab. *If a patient enters extension phase, follow Appendix 1-B for study completion or early discontinuation safety follow up.*
- ^e Obtain written informed consent (or patient's assent and caregiver written informed consent if patient is an adolescent/pediatric) before distribution of electronic, handheld device and collection of any data. Patients will be enrolled and randomized after giving informed consent, and assent when appropriate.
- ^f Collected from patient medical records and documented on the eCRF, including information on target joint(s).
- ^g Calculation of dose based on weight is required. A complete physical examination will be performed at screening and at least a targeted physical examination will be performed at subsequent visits. Targeted physical examination of joints (for bleeds, evidence of arthropathy) and skin (for bruises, hematomas, and injection-site reactions) as clinically indicated and/or with report of new or worsening adverse event.
- ^h Body temperature (oral or tympanic), blood pressure, pulse rate, and respiratory rate only to be used to monitor hypersensitivity reactions during and after injection and not to be entered on eCRF, except at Weeks 1, 25, 49, study completion/early termination, and at the Early Discontinuation Safety Follow-up visit before study completion (i.e., 24 weeks after discontinuing emicizumab for patients in Arms A and B and at Week 73 for patients in Arm C). Weight will be measured and recorded in the eCRF at each clinic visit prior to any injections (if applicable.) Height will be measured at screening and annually.

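### The switch-day cutoff leaves Arm C with no routinely scheduled, recorded control-period laboratory, ECG or vital-sign value after Week 1

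*Protocol*

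**What the plan says.** The safety objective for the randomized arms in Protocol Table 2 is comparative: "To evaluate the overall safety of prophylactic emicizumab compared with no prophylaxis in patients with hemophilia A". Its endpoints, listed for Arm C as well as the emicizumab arms, include the incidence of laboratory abnormalities and "Changes in physical examination findings and vital signs".

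Protocol 6.5 divides Arm C data by calendar date. "For Arm C patients, all safety data reported up to the day prior to switching will be included in the" control-arm summaries, and "all safety data reported on or after the date of switching to active treatment will be reported separately". The same section plans laboratory summaries by arm and shift tables from baseline. SAP 4.7.3 to 4.7.5 plan laboratory shift tables, vital-sign change from baseline by arm over time, and ECG change from baseline by arm and visit.

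The table headed "Schedule of Assessments—Arm C (Screening to Switch to Emicizumab") has visits at screening and Weeks 1, 5, 9, 13, 17 and 21. The continuation table starts at Week 25 and marks emicizumab administration at that visit. The Appendix 1-A notes add: "Clinic visits should coincide with the day of emicizumab dosing, and on those days the dose should be administered after blood draws" and the other assessments. Footnote h says temperature, blood pressure, pulse and respiratory rate are "not to be entered on eCRF, except at Weeks 1, 25, 49" and at completion, early-termination or safety follow-up visits.

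Section 3.1 says that physical examinations, vital signs, ECGs and laboratory assessments "will be collected as per the schedule of assessments and will be the same for all patients", excepting only PK and ADA in Arm C before the switch.

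**The concern.** Each rule is reasonable alone; the difficulty comes from combining them. The pre-switch table is sparse because Arm C receives no study drug. Footnote h limits data entry to a few landmark visits. The 6.5 cutoff is meant to keep on-drug data out of the control column. But the one landmark visit at which Arm C has a full set of assessments after 24 weeks without prophylaxis is also the first dosing day. A cutoff set by date rather than by dose time discards that set from the control arm, although it was collected before any drug was given.

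At stake are the by-arm change-from-baseline tables. For patients who switch on schedule, the control column would show a baseline and no scheduled follow-up, so drift over 24 weeks on emicizumab could not be set against drift over 24 weeks without it. A reader relying on Section 3.1 would also assume that the arms were examined equally often, which the schedules contradict.

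**Working it through.** The plan states no figure for this, so the check is a count of scheduled assessments followed by two rules.

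**Step 1: Arm C assessments after Week 1 and before the switch date** (Appendix 1-A, Arm C pre-switch table). Laboratories, ECG and physical examination are marked at screening and Week 1 only. Footnote k makes the Week 1 ECG conditional on an abnormal screening ECG and times later ECGs from the start of emicizumab. Vital signs and adverse events are marked at Weeks 5, 9, 13, 17 and 21, which is 5 visits.

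**Step 2: eCRF rule** (footnote h). None of those five weeks is among the recording visits, so 5 measured sets of vital signs yield 0 recorded ones. Weight is recorded at every visit, but the vital signs in SAP 4.7.4 do not include it.

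**Step 3: switch-day rule** (Protocol 6.5). All four domains are next marked at Week 25, the first dosing day. Under the Appendix 1-A notes the dose follows the assessments; Sections 4.5.4 and 4.5.5 say the same for vital signs and laboratory samples. The values precede exposure but carry the switch date, so they leave the control arm.

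| Domain | Arm C, measured Weeks 5–21 | Recorded as control data under 6.5 | If pre-dose Week 25 counts as control |
|---|---|---|---|
| Safety laboratories | 0 | 0 | 1 |
| ECG | 0 | 0 | 1 |
| Temperature, blood pressure, pulse, respiratory rate | 5 | 0 | 1 |
| Physical examination | 0 in the table; other text conflicts | unresolved | at least 1 |
| Adverse events | 5 | 5 | not affected |

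**Step 4: Arms A and B over the same 24 weeks.** The schedule has ten columns after Week 1 up to Week 25 (Weeks 2, 3, 4, 5, 7, 9, 13, 17, 21 and 25). As read from the PDF, the laboratory row is one cell shorter than its header, so the count is 9 or 10. Footnote k gives 2 ECGs after the start of emicizumab, at 4–8 and 24 weeks. Footnote h gives 1 recorded set of vital signs, at Week 25.

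After restoring Week 25 to the control arm, recorded timepoints per patient in Arms A/B versus C would be 9–10 versus 1 for laboratories, 2 versus 1 for ECG, and 1 versus 1 for vital signs. Week 25 is thus the timepoint the arms share. With 14 control patients planned, it yields at most 14 control values per parameter.

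**The case against.** The strongest reply is that the comparison with no prophylaxis is mainly one of adverse events. Section 6.5 attaches the comparative wording to adverse-event incidence and gives the other domains descriptive summaries without tests. Adverse events are collected at every Arm C visit. Significant laboratory, vital-sign, ECG and examination findings are reportable as adverse events under Sections 5.3.5.5, 5.3.5.6, 4.5.6 and 4.5.3. This stands, and it limits the loss. It does not fill the shift and change tables, because a silent abnormality is reported only if someone tests for it.

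A reader might infer that Arm C has no control-period data at all in these domains. The documents do not support that:

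- Section 4.5.5 requires platelets, creatinine, LDH, smear, fibrinogen and D-dimer after bypassing-agent use and does not restrict this to emicizumab recipients. Non-inhibitor enrolment is capped at 55 of 70, so some Arm C inhibitor patients may contribute. These tests follow events, cover a subset, and have no row in the Arm C pre-switch table. Unscheduled tests are also allowed.
- Section 4.5.3 and footnote g call for at least targeted examinations at visits after screening, while the Arm C table marks none after Week 1. That is a conflict to resolve, not proof that none is planned.

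Nor are the Week 25 values lost; they are reported in another column. The SAP does not repeat the day-before rule for safety. Its safety populations (4.2.5) carry no date cutoff, and SAP 4.1 describes the control period simply as the first 24 weeks. That makes the correction easy, but the only explicit rule remains the one in Protocol 6.5.

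Finally, a reader might put a percentage on the bias in counts of patients ever abnormal. The documents give no per-test rate, and repeated tests in one patient are not independent. Only the direction is clear: more testing finds more abnormalities.

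**Conclusion.** The point holds for safety laboratories, ECG and the four vital signs that SAP 4.7.4 analyses together with blood pressure and temperature, namely pulse, respiratory rate, temperature and blood pressure. For Arm C patients who switch at the Week 25 visit, there are 0 routinely scheduled, recorded control-period values after Week 1, although a valid pre-dose set at 24 weeks is collected. For physical examination the finding is an unresolved conflict between passages.

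It would go too far to say that the safety comparison as a whole fails. Adverse events remain comparable, the affected summaries are descriptive, and primary efficacy is untouched. The change is still worth making: these are listed endpoints with planned by-arm tables, and a rule in the plan, not a lack of data, empties the control column.

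The conclusion assumes that Week 25 assessments precede the first dose on the same day, as the notes require. A patient whose first dose falls on a later day keeps those values in the control period. It also assumes that Week 1 is baseline or near it; the SAP defines no baseline, but Week 1 represents no follow-up without prophylaxis in any case. If Section 3.1 governed over the schedule, the gap in assessments would close, so the two must be reconciled.

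**What to change.** 1. In Protocol 6.5 and SAP 4.2.5 and 4.7, assign any Arm C assessment made on the switch date before the first emicizumab dose to the control period. It may also serve as the baseline for the Arm C emicizumab period.
2. Present the between-arm change from baseline for these domains at Week 25.
3. Where counts of patients ever abnormal are shown by arm, add a note that testing was unequal: about 9–10 laboratory visits after Week 1 in Arms A and B against 1 in Arm C. Whether to show such counts beside Arm C at all is the sponsor's choice.
4. Reconcile the Section 3.1 sentence with the Arm C schedule, and reconcile that schedule with Section 4.5.3 and footnote g on later examinations.

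The cost is wording in two documents and one derivation using dose and assessment times; no visits or samples are added. The drawback is that each Week 25 value serves two summaries, as the end of the control period and the start of the emicizumab period, which should be footnoted. The fix adds one timepoint only; Weeks 5 to 21 would still have no scheduled, recorded control values in these domains.

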5.3.1 Adverse Event Reporting Period

Investigators will seek information on adverse events at each patient contact. All adverse events, whether reported by the patient or noted by study personnel, will be recorded in the patient's medical record and on the Adverse Event eCRF.

After informed consent has been obtained but prior to randomization (randomized arms) or initiation of study drug (non-randomized arm), only serious adverse events caused by a protocol-mandated intervention (e.g., invasive procedures such as biopsies, discontinuation of medications) should be reported (see Section 5.4.2 for instructions for reporting serious adverse events).

After randomization (randomized arms) or initiation of study drug (non-randomized arm), all adverse events will be reported until the patient completes his or her last study visit. After this period, the investigator should report any serious adverse events that are believed to be related to prior study drug treatment (see Section 5.6).

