Appendix 1-A (cont.) Schedule of Assessments

Schedule of Assessments—Arm C (Continued, at Time of Switch to Emicizumab)																		
	Wk 25	Wk 26	Wk 27	Wk 28	Wk 29	Wk 31	Wk 33	Wk 37	Wk 41	Wk 45	Wk 49	Q12W from Wk 61	Wk 73	Wk 85	Daily/weekly ^b	Study Comp/ET ^c	Early Disc. Safety F/U Visit before Study Comp ^d	
Physical examination (including weight) ^g	x				x						x			x			x	x
Vital signs ^h	x ^h	x	x	x	x		x	x	x	x	x ^h	x	x ^h	x		x ^h	x	
Height	x										x		x					
Serum pregnancy test ⁱ	x																	
Urine pregnancy test ⁱ	x				x		x	x	x	x	x	x	x	x		x	x	
Concomitant medications ^j	x				x		x	x	x	x	x	x	x	x		x	x	
ECG ^k	x				x ^k						x						x	
Safety laboratory assessments ⁱ	x	x	x	x	x	x	x	x	x	x	x	x	x	x		x	x	
Bleed/medication questionnaire ^l															x			
Bleed/medication data review ^s	x				x		x	x	x	x	x	x	x	x		x	x	
Adverse events ^m	x	x	x	x	x	x	x	x	x	x	x	x	x	x		x	x	
IMP management ⁿ	x	x	x	x	x	x	x	x	x	x	x	x	x	x		x		
HRQoL and health status ^o	x						x				x		x	x		x		
Emicizumab administration ^p	x	x	x	x	x		x	x	x	x	x	x	x	x				
PK/PD/ADA assessment ^q	See Appendix 2-A for details																	
Following treatment with bypassing agents ^r	Monitoring for thromboembolic events and thrombotic microangiopathy ^r																	

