Appendix 1-A (cont.) Schedule of Assessments

- ⁱ Laboratory data (performed locally) include: complete blood count with differential (i.e., neutrophils, hemoglobin, platelet count), serum chemistries (i.e., sodium, potassium, glucose, blood urea nitrogen, creatinine, calcium, phosphorus, magnesium, total and direct bilirubin, albumin, alanine aminotransferase, aspartate aminotransferase, and alkaline phosphatase). Laboratory assessments completed at the screening visit do not have to be repeated at Week 1, if the period between screening and Week 1 is 5 days or less and there has been no change in health status as assessed by the investigator. Patients with childbearing potential will be required to have a negative serum pregnancy test result at screening (and within 7 days of study drug initiation, if applicable) and urine pregnancy tests performed at every clinic visit, with the exception of Weeks 2–4 and 7. Patients on Arm C will have urine pregnancy test performed at screening and before starting emicizumab (Week 25).
- ^j Concomitant medications (e.g., extra pain medication with bleed) will be asked about at the time of the monthly assessment, excluding treatments for bleeds (i.e., FVIII and other medications to treat bleeds), which will be collected on the bleeding questionnaire.
- ^k Performed locally. If screening ECG is abnormal, repeat at Week 1 (or Week 2 if screening and Week 1 occur on the same day), otherwise do not repeat. ECGs will also be performed 4–8 and 24 weeks after starting emicizumab or dose up-titration, as well as at study completion/early termination.
- ^l Reported by the patient or their caregivers and includes: start date and time, reason, type, location, and associated symptoms for joint and muscle bleeds, as well as start date and time, reason, type, and dose of each injection, excluding emicizumab.
- ^m Injection-site reaction adverse events will be collected on a separate form from the adverse event form. If there is unexpected worsening of the patient's hemophilia in terms of severity (e.g., increased number of doses of FVIII to stop bleeds compared with before study entry), frequency of bleeds, or nature at any time during the study, this should be documented as an adverse event on the Adverse Event eCRF, conveying that the underlying condition has changed by including applicable descriptors (e.g., "increased clinical severity of hemophilia").

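### Protocol 6.5 divides Arm C safety data at the switch by date reported, not onset, so adverse events from the untreated weeks before Week 25 can fall in the emicizumab period

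*Protocol*

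**What the plan says.** Protocol 6.5 divides Arm C safety data at the switch. On one side, "all safety data reported up to the day prior to switching will be included in the 'control arm' safety summaries". On the other, "all safety data reported on or after the date of switching to active treatment will be reported separately". The dividing criterion in both halves is when the data were reported.

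On collection, Protocol 5.3.1 states: "Investigators will seek information on adverse events at each patient contact". Appendix 1-A has two Arm C tables. The one running up to the switch has its last adverse-event check at Week 21. The one starting at the switch begins at Week 25, with an adverse-event check and emicizumab administration at the same visit. The general notes to Appendix 1-A place the dose after that day's blood draws and other assessments.

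SAP 4.1 says the two Arm C periods are analysed separately and includes post-switch Arm C in the All Emicizumab safety outputs with Arms A and B. SAP 4.2.5 defines SAF1 and SAF2 by which patients they contain, not by how events are allocated. SAP 4.7.2 summarises adverse events by treatment arm and has no onset or treatment-emergent rule.

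**The concern.** The safety objective for Arms A, B and C compares emicizumab with no prophylaxis. An event that began before any emicizumab was given belongs to the control experience whenever it was written down. A split on reporting date does not guarantee this. The risk is greatest in the last control interval, because the visit that closes that interval is also the switch date.

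Two summaries would be affected. The control arm, planned at only 14 patients, would lose events. The post-switch Arm C and pooled emicizumab summaries would gain events from untreated time, which blurs the reading of early events after the first dose.

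**Working it through.** The plan states no figure here to reproduce. The check is of wording against schedule, followed by person-time arithmetic.

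**Inputs from the documents**
- Control period: 24 weeks = 168 days (Protocol 3.1 and 4.3.2).
- Last pre-switch adverse-event check at Week 21, next at Week 25 (Appendix 1-A, Arm C tables): scheduled gap 28 days.
- Visit window after the first 3 months: ±7 days (Appendix 1-A notes). The gap can therefore run from 14 to 42 days.
- Planned patients: 14 in Arm C and 28 in each of Arms A and B (Protocol 6.1, SAP 2.4).

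**Assumptions, not in the documents**
- The adverse-event rate is constant and the same on and off emicizumab (true ratio 1.0).
- All 14 Arm C patients switch at 24 weeks, and the control period is held at 168 days.
- A share *s* of events starting in the gap is first recorded at the switch visit. The range shown is 0.25 to 1.

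**Step 1: follow one event.** A non-serious event starts in Week 23. The example questions in Protocol 5.3.2 ask about the time since the last visit, so at Week 25 they cover the untreated interval. The event is elicited before the dose but on the switch date. Under the 6.5 wording it is post-switch data. The bleed and medication questionnaire is not another route, because Protocol 5.3.5.13 keeps patient-reported data out of adverse-event reporting.

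**Step 2: share of control events moved** = gap × *s* / 168.

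**Step 3: apparent ratio, Arm A or B versus control** = 1 / (1 − share moved). Arms A and B are themselves unchanged.

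| Gap (days) | *s* | Share moved | Apparent ratio |
|---|---|---|---|
| 28 | 0.25 | 7/168 = 4.2% | 1.04 |
| 28 | 0.5 | 14/168 = 8.3% | 1.09 |
| 28 | 1 | 28/168 = 16.7% | 1.20 |
| 14 | 1 | 14/168 = 8.3% | 1.09 |
| 42 | 1 | 42/168 = 25.0% | 1.33 |

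These ratios concern event counts per unit of time. The percentage of patients with at least one event would normally move less, since a patient with an event recorded earlier in the control period stays counted.

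**Step 4: effect on the pooled emicizumab summaries.** At the scheduled gap, at most 14 × 4 = 56 patient-weeks of events are added. Arms A and B alone have (28 + 28) × 24 = 1,344 planned patient-weeks. The inflation is at most 56 / 1,344 = 4.2%, before any post-switch Arm C exposure enters the denominator. With a further 14 × 24 = 336 patient-weeks it is 56 / 1,680 = 3.3%.

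**Step 5: effect of an onset rule.** No control-onset event moves, and a true ratio of 1.0 is shown as 1.0.

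**The case against.** The strongest reply is that *reported* is loose wording for *occurring*. The sentence before it in Protocol 6.5 groups patients by treatment actually received. SAP 4.1 defines the Arm C periods by whether the patient is on no prophylaxis or on emicizumab. SAP 2.3.1.1 ends the first Arm C efficacy period for bleeds on the day before the first dose. The adverse-event dates the protocol describes are start, resolution and becoming serious; no report date is named as an analysis variable. A programmer might well use the start date without being told.

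This is plausible and cannot be ruled out. It does not remove the point, because neither document says it for adverse events and the one explicit rule says something else. Even on the loose reading, the boundary is the switch date rather than the first dose, so a same-day pre-dose finding still falls post-switch.

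Second, capture may not wait for Week 25. Protocol 3.1 expects adverse events to be captured as they occur, 5.3.1 refers to contacts rather than scheduled visits, and Appendix 1-A allows unscheduled assessments. Serious events and events of special interest are due within 24 hours of the investigator learning of them. This stands: the problem mainly concerns non-serious events, and 16.7% is a ceiling for the scheduled gap.

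Third, the consequences are limited. The randomized layout in SAP 4.1 compares A and B with Arm C before the switch, so no event is added to A or B there. Any error makes the drug look worse rather than hiding a signal. Investigators judge causality partly on when the event began relative to starting the drug (Protocol 5.3.4), and relatedness is summarised separately (SAP 4.7.2). This also stands.

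**Conclusion.** The point holds as a defect in a stated rule. Taken as written, Protocol 6.5 can place events from untreated time in the post-switch set, and nothing in SAP 4.1, 4.2.5 or 4.7.2 corrects it.

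At the scheduled gap, at most 16.7% of control-period events are affected, with a range of 8.3% to 25% across the visit windows. If rates are truly equal, the control undercount alone could make Arm A or B versus control appear as up to 1.20 at that gap, while the pooled emicizumab count rises by no more than about 4%. These are ceilings. They assume a constant rate, that all 14 patients switch, and that nothing starting after Week 21 is recorded before Week 25. Safety is summarised descriptively, so no test, alpha or power is involved.

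A reader might go further and infer that a sixth of control events will be counted as emicizumab events and that the randomized safety comparison is loaded from both sides. The documents do not support that. They do not establish that report date will be the programmed variable or that events go unrecorded until Week 25. In the randomized layout only the control side can change. Nor can a number of moved events be given, since the documents state no adverse-event rate per unit of time for this trial.

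**What to change.** In Protocol 6.5, replace *reported* with *with onset*, and make the first emicizumab dose the boundary. Put the same rule in SAP 4.7.2: an Arm C adverse event with onset before the first dose is control, whenever it was recorded, and one with onset at or after the first dose is emicizumab. Events elicited at the pre-dose Week 25 assessment count as control.

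The cost is about one sentence in each document. Adverse-event start dates are already recorded (Protocol 5.3.5.2). Onset time is not shown to be collected for adverse events. If it is not, a pre-dose flag on events dated to the switch day is enough.
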